9.4 Receipt and return of LUM015 and the LUM Imaging Devices

A drug inventory will be maintained by the clinical site's pharmacy. The inventory will include details of the LUM015 received and a clear record of when dispensed and for which subjects. This inventory record shall indicate the quantity and disposition of all investigational materials on hand at any time during the study.

LUM Imaging Devices will be assembled by Lumicell personnel and Instructions For Use (IFU) will be provided. Lumicell personnel will train the clinical staff on using the LUM Imaging System. Each clinical site investigator will maintain a device accountability record to document receipt and return of the LUM Imaging Devices.

At the end of the study, unused supplies of LUM015 and the investigational devices must be returned to Lumicell. A Lumicell representative will advise you when to return the supplies, as well as the proper shipping methods. Any LUM015 destroyed according to institutional policies will be documented. LUM015 should only be destroyed instead of returning to Lumicell if written instruction to do so is provided by Lumicell.

10 Schedule of Events

LUMICELL CONFIDENTIAL

This document is confidential. Do not disclose or use except as authorized.

Baseline evaluations are to be conducted within 8-weeks prior to subject enrollment. The breast cancer diagnosis is not considered a baseline evaluation. All baseline assessments must be performed prior to administration of any study agent.

Table 2: Schedule of events.

	Pre-Enrollment /Screening	Day 1 / Enrollment	~2-14 days after surgery	Routine follow up visit	3-month PROM survey collection	6-month PROM survey collection
Informed consent	X					
Medical History	X					
Radiologic evaluation*	X					
Physical exam (Ht, Wt, VS)	X					
Pregnancy test (serum or urine)	X ^b					
CBC with differentials	X			X		
Serum chemistry ^a	X			X		
Concomitant Medications	X	X		X		
Adverse event/adverse device effect evaluation		X		X		
Patient Reported Outcome Measures Survey**		X**		X	X	X
LUM015 administration		X				
Randomization		X				
Intraoperative imaging***		X				
Margin assessment			X			

*: Radiologic Evaluations are not required if not part of the patient's medical history

** : PROs are optional for enrollment. The baseline evaluation can be completed by the subject at any time prior to the lumpectomy procedure. A validated survey tool, the Breast-Q, will be used to collect the majority of the PROMs.

***: If subject is randomized into the device arm

a: Albumin, alkaline phosphatase, total bilirubin, BUN, calcium, chloride, glucose, potassium, total protein, SGOT [AST], SGPT [ALT], sodium and creatinine/creatinine clearance.

b: Serum or urine pregnancy test (women of childbearing potential)

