7 SUBJECT ENROLLMENT

7.1 General guidelines for screening and enrollment

Patients who have consented to participate in the study will be screened against the eligibility criteria. Patients who do not meet the inclusion/exclusion criteria listed in the protocol will fail screening and not be eligible to participate in the study. The subject is not considered enrolled into the study until written Informed Consent is obtained, the patient is confirmed as eligible per inclusion and exclusion criteria, and the investigational product has been administered (Study Day One).

Clinical sites are asked to keep comprehensive Screening and Enrollment logs and provide these logs to Lumicell on a regular basis.

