7.2 Enrollment process

Patients who consent to participate in this study should be evaluated for eligibility. All patients who consent should be entered into the electronic data capture (EDC) system. Screening procedure data should be recorded in the EDC. The site study team should notify Lumicell of a potential candidate for the study and expected surgery date after the subject has been consented.

The enrollment procedures are as follows:

1. Obtain written informed consent from the subject prior to the performance of any study related procedures or assessments.
2. Assign the subject a study subject ID number and enter the subject in the EDC. The numbers should follow the Lumicell assigned format as described at the Site Initiation Visit in compliance with the Case Report Form nomenclature. All patients who consent should be entered into the electronic data capture (EDC) system.
3. Confirm protocol-specific eligibility using the eligibility assessment documented in the subject's medical/research record. **To be eligible for enrollment to the study, the subject must meet each inclusion and have none of the exclusion criteria listed in the eligibility section of this protocol.**
4. Notify Lumicell clinical team of eligible subject status and date of proposed surgery.
5. The subject is considered 'enrolled' once they have been administered LUM015 (day of surgery)

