8.5 Criteria for removal from the study

Subjects will be removed from study when any of the criteria listed in Section 6.2 applies. The reason for study removal and the date the subject was removed must be documented in the study-specific case report form (CRF). A subject removed from the study will be given standard of care treatment. Subjects removed from the study prior to dosing do not count toward total enrollment numbers; they are considered “screen failures”.

Individual patients may be discontinued from the study by the Investigator or Lumicell at any time if either determines that it is not in the best interest of the patient to continue (e.g., continuation in the study represents a serious medical risk to the patient). This may include, but is not limited to, the presence of serious, life-threatening adverse events, unanticipated adverse device effects, adverse events, or adverse device effects that are unacceptable in nature, severity, or frequency as assessed by the Investigator.

Patients must not be enrolled if, prior to study drug injection, they become pregnant or withdraw consent. While patients will be encouraged to complete the study, they may voluntarily withdraw at any time.

In the event of unusual or life-threatening complications, participating investigators must immediately notify Lumicell.

LUMICELL CONFIDENTIAL

This document is confidential. Do not disclose or use except as authorized.

An individual is considered to be a participant once she is enrolled or entered into the study. This would include subjects that are eligible for contributing data to the scientific aims and consented for participation, including individuals who subsequently dropout. Subjects who are screened for participation but are not eligible (because of not meeting inclusion/exclusion or because LUM015 was not injected) or who do not consent would not be considered as participants.

Prospective exclusions from the efficacy analysis population will include: 1) patients for whom the LUM015 systemic injection was not performed properly and (2) major protocol deviations. These patients will be included in the safety analysis cohort.

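### The only scheduled pregnancy test may be up to 56 days old when LUM015, an agent of unknown teratogenicity, is injected; require a negative result on Day 1 or shortly before dosing.

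*Protocol*

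**What the plan says.** Protocol Section 10 gives two timing limits for baseline evaluations. The first is "Baseline evaluations are to be conducted within 8-weeks prior to subject enrollment". The second is "All baseline assessments must be performed prior to administration of any study agent". Neither limit is tightened for any individual test.

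In Table 2 the row beginning "Pregnancy test (serum or urine" carries one mark, in the screening column. Footnote b to that row says who is tested, "Serum or urine pregnancy test (women of childbearing potential", and adds no timing.

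Enrolment is tied to dosing. Section 7.1 counts a subject as enrolled only when, besides consent and eligibility, "the investigational product has been administered (Study Day One". Section 7.2 step 5 agrees: the subject is enrolled "once they have been administered LUM015 (day of surgery".

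Several provisions bear on pregnancy before dosing:

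- Section 6.2.2 excludes women pregnant at diagnosis and gives the unknown teratogenicity of LUM015 as the reason.
- Section 6.2.3 excludes sexually active women unwilling or unable to use two contraceptive methods until 60 days after injection, and asks a woman who suspects pregnancy to tell her physician.
- Section 8.5 states: "Patients must not be enrolled if, prior to study drug injection, they become pregnant or withdraw consent".

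**The concern.** The protocol treats fetal exposure as a hazard. It excludes pregnancy, asks for contraception for 60 days after the dose, and bars enrolment of anyone who becomes pregnant before the dose. LUM015 is a single injection that cannot be undone. Yet the only objective check is placed where it can be weeks out of date by the time of injection.

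A pregnancy that begins, or becomes detectable, after the screening test and that the woman has not recognised would meet no scheduled check before dosing. At stake is the safety of participants of childbearing potential. The efficacy results are not affected.

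**Working it through.** **Inputs**

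- Baseline window: 8 weeks before enrolment (Protocol Section 10).
- End of the window: enrolment, which is LUM015 administration (Protocol 7.1 and 7.2).
- Scheduled pregnancy tests: one, at screening (Table 2 and footnote b).
- Enrolled: 406 (SAP 1.1; SAP dated 17NOV2021).
- Enrolment cap: 450 (Protocol Section 1, the revision note in Protocol 15.3.3, and SAP 4.5).

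**Step 1: maximum age of the test at injection.** Because the window is counted back from enrolment, and enrolment is the injection,

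maximum age = 8 weeks × 7 days per week = 56 days.

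**Step 2: does anything on Day 1 shorten this?** Table 2 marks six rows in the Day 1 column: concomitant medications, adverse event evaluation, the patient-reported outcome survey, LUM015 administration, randomization and intraoperative imaging. The pregnancy test is not among them. The injection procedures in 5.2.3, 8.1 and 9.2 do not call for a test either.

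**Step 3: does any other provision require a later test?**

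- Section 7.2 step 3 reads "Confirm protocol-specific eligibility using the eligibility assessment documented in the" subject's record. That record can rest on the screening test.
- The lead-in to 6.2 assesses the exclusions at screening. The 8.5 rule on removal when a 6.2 criterion applies therefore adds no pre-dose test.
- Section 6.2.3 relies on contraception and on the woman's own report. Neither detects a pregnancy she has not recognised. Its starting point, entry to the study, is also not clearly tied to the date of the screening test.
- Section 6.2.12 allows investigator discretion but mandates no test.
- Section 8.5 supplies the prohibition without a means of detection.

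**Step 4: effect of the change.** With a Day 1 test the maximum age falls from 56 days to 0. With a 3-day window it falls from 56 to 3.

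**Step 5: who could still benefit in this trial.** Further patients who can be injected under the cap: 450 − 406 = 44 at most, of any age and menopausal status. If 406 is the final number, it is 0.

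The 44 counts injected patients, not tests. Section 8.5 leaves subjects removed before dosing out of the enrolment total, so a woman tested and then not dosed falls outside it. A postponed operation can also require a second repeat. The 44 is therefore not an upper bound on the number of added tests.

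**The case against.** The strongest objection is that the change may come too late. SAP 1.1 speaks of the 406 patients enrolled, which reads most naturally as a completed count. The revision note in Protocol 15.3.3 says an April 2021 event count pointed to 380 patients for the 70 required events, and 406 exceeds that. If enrolment has ended, no woman in this trial gains. This stands as a limit on the benefit. It does not make the schedule adequate: the documents do not say that enrolment has closed, and the protocol still allows up to 450.

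The second objection is that the operative rule already exists. Section 8.5 bars enrolment of a woman who becomes pregnant before injection, and because enrolment is injection, that duty runs to the moment of dosing. Contraception, self-report, eligibility confirmation and investigator discretion add to it. This stands in part. A reader might infer from 6.2.2, which speaks only of pregnancy at diagnosis, that the protocol allows a woman known to be pregnant to be injected. It does not, because 8.5 closes that reading. What remains is the unrecognised pregnancy arising or becoming detectable between test and injection. There, following the schedule as written gives weaker protection than 8.5 intends.

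Third, 3 days has no source in the documents. That is correct; only a test closer to dosing is supported.

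Finally, hospitals may test before surgery under their own rules, and Section 9 refers to a Pharmacy Manual that is not among the documents reviewed. The point therefore concerns the protocol text, not what sites actually do.

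**Conclusion.** The concern holds as a gap in participant protection. The protocol permits injection of an agent of unknown teratogenicity on a negative pregnancy test up to 56 days old, and no scheduled check supports its own rule in 8.5. The 56-day figure follows directly from Section 10 with 7.1 and 7.2 and needs no outside assumption.

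Two stronger readings are tempting and not supported. One is that tests are commonly that old at dosing: 56 days is only the permitted maximum, and the usual interval from screening to surgery is not given. The other is that a particular number of women is exposed to this risk: the documents do not give the number of women of childbearing potential.

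The gain in this trial is confined to women not yet injected. They are some part of at most 44 further patients, and none if 406 is final. The change is still worth making while any patient remains to be dosed, because it is specific, cheap and serves a rule that the protocol already states.

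**What to change.** In Section 10 and Table 2, exempt the pregnancy test from the 8-week baseline window. For women of childbearing potential, require a negative serum or urine result on Day 1 before LUM015 injection, or within a short stated window before it. Three days is a reviewer's proposal; the sponsor may choose another short limit. A screening test inside the window counts; otherwise it is repeated. As a consistency edit only, reword 6.2.2 to cover pregnancy at any time up to injection, in line with 8.5.

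The cost is protocol wording and usually one repeat urine or serum test per woman of childbearing potential not yet injected, occasionally more if surgery is postponed. No firm upper bound on the number of tests is claimed. A Day 1 test needs no added visit, because LUM015 is already given at the surgical center or hospital that day (8.1). The main drawback is a few late screen failures close to surgery. Endpoints, sample size, significance levels and analyses stay as they are.

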11 SAFETY

A Phase 1 IND study in sarcoma and breast cancer patients was completed at Duke University Medical Center. The primary endpoint of this study was to evaluate the safety of the LUM015 drug component. As a secondary endpoint, the signals from normal and tumor tissue were measured ex vivo using the LUM Imaging Device component. Twelve (12) sarcoma patients and three (3) breast cancer patients (invasive ductal carcinoma) were injected with LUM015 at doses ranging from 0.5 mg/kg to 1.5 mg/kg with no adverse pharmacological activity reported. The only noticeable effect in the study subjects was blue/green discoloration of urine, which resolved within 12-24 hours post injection for most patients.

Three feasibility studies have been completed in breast cancer with 294 patients enrolled (n=15 in Phase A, n=45 in Phase B, n=234 in Phase C), with 289 patients injected with LUM015. One patient enrolled in Phase B experienced blue discoloration at the injection site due to extravasation of LUM015 resulting from incorrect positioning of the intravenous catheter. After 92 days from injection, the blue discoloration disappeared but slight pallor of the skin at the injection site remained. One patient, with known hypersensitivity to contrast agents enrolled in the Phase C study experienced an anaphylaxis reaction to the LUM015 injection. The patient recovered in <24 hours.

11.1 LUM015 pharmacokinetics

During the Phase 1 IND study, the first 3 eligible subjects were dosed at 0.5mg/kg LUM015 and the second 3 subjects were dosed at 1.0mg/kg LUM015, with both groups injected ~29 hours prior to surgery. Resected tissue was imaged with the LUM Imaging Device in the pathology suite. A comparison of pharmacokinetic data from the initial 6 subjects to preclinical mouse studies suggested that a higher tumor:normal signal ratio would be achieved if tissue were imaged 4-6 hours after injection. The next 3 subjects were injected with 1.0mg/kg of LUM015 and followed by 3 subjects injected with 1.5 mg/kg of LUM015 and the final cohort of 3 subjects was injected with 0.5mg/kg. These nine subjects were followed by surgical resection at approximately 6 hours after LUM015 injection (i.e. same day injection and surgery).

To evaluate the pharmacokinetic parameters of LUM015, plasma PK samples were collected at the following time-points: pre-dose, 10, 20 minutes, 1, 2, 4, 8, 12, 18, 22, and 48 hours post-dose. The 48-hour collection was optional. Analysis of LUM015 (as Frag 1 after trypsin digestion of plasma) and Fragment 1 (non-digested plasma) were measured by LC-MS/MS. Additional metabolites, Fragment 2 and Fragment 3 were measured by HPLC-fluorescence.

A non-compartmental approach within Win-Nonlin software was used for PK parameter estimation. Due to a relative complexity of the PK profile observed and data constraints inherent in the study (small number of patients per dose level, optional data from 22-48 hours), a compartmental modeling approach was not utilized. Out of the 15 subjects, the 48-h time-point sample was collected in 9 patients. Thus, in order to make use of the wealth of data collected up to 22 hours (all 15 patients from the study), but also use potentially important 48-hour data from the limited set of 9 subjects, PK calculations were performed on both sets (22-hour and 48-hour) independently. A summary of the resulting PK parameters for LUM015 are presented in Table 3.

Table 3: Pharmacokinetic parameters for LUM015. SD = standard deviation.

PK Parameter	0.5 mg/kg (SD)	mg/kg (SD)	1.5 mg/kg (SD)
--------------	----------------	------------	----------------

LUMICELL CONFIDENTIAL

This document is confidential. Do not disclose or use except as authorized.

Tmax [hr]	0.11 (0.17)	0.06 (0.13)	0.00 (0.00)
Cmax [ug/mL]	15.46 (2.26)	28.41 (6.55)	45.76 (3.78)
AUClast [ug mL-1 h]	78.36 (12.91)	159.65 (45.94)	252.08 (57.98)
T1/2 [h]	5.21 (1.33)	5.08 (0.86)	5.42 (0.67)

The pharmacokinetic data support rapid clearance of LUM015. After 22 and 48 hours, only 5% and 2% of the parent drug remain in plasma, respectively. The PK data support a multi-phased profile with linear pharmacokinetics.

11.2 Expected adverse events (associated with LUM015)

During Phase C of the Feasibility Study, one patient had an anaphylactic reaction to the LUM015 injection. This patient had a history of allergic reactions to contrast agents. The event was resolved within 24 hours of occurrence. We now consider anaphylactic reaction an expected adverse event, with occasional occurrence and serious severity. Table 4 below lists the expected adverse events due to LUM015 injection with their estimated occurrence and severity.

Table 4: List of expected adverse events due to LUM015 administration.

Adverse Events (Drug Related):	Occurrence:	Severity:
LUM015 extravasation	Occasional	Minor
Chromaturia	Frequent	Negligible
Anaphylaxis/hypersensitivity	Occasional	Serious

No adverse events related to the administration of LUM015 were observed during the Phase 1 IND safety study. Temporary blue/green discoloration of the urine was noted in these patients due to the blue color of LUM015. Prior to the Phase 1 study, LUM015 had not previously been used in humans. Lumicell's preclinical studies demonstrated that it was reasonably safe to proceed with a Phase 1 IND study in humans. Preclinical studies in rats showed no LUM015 related effects on clinical observations, FOB evaluation, body weights, food consumption, ocular condition, clinical chemistry, hematology and coagulation parameters or organ weight at doses up to 53-fold higher than in humans.

The results from the repeat dose toxicity study in dogs (performed by NCI) show that administration of 0.5 or 10.0 mg/kg of LUM015 intravenously once daily for seven consecutive days (8 total doses) did not cause any observable target organ toxicities. The only observable effect was hypersensitivity in several dogs.

The results from a repeat dose toxicity study in rabbits show that administration of 15 mg/kg of LUM015 intravenously one daily for seven consecutive days was well tolerated. The test article-related findings were limited to transient blue/green discoloration of the urine. There were no test article-related adverse events observed and no hypersensitivity was seen.

Additional information is available in the Investigator's Brochure for LUM015.

Clinicians should be prepared for a possible hypersensitivity or allergic reaction to occur during each administration of LUM015. Standing orders should be in place in the event of a hypersensitivity or allergic reaction for immediate intervention including administration of

diphenhydramine, prednisone or both. If a study subject develops a Grade 3 (or greater) allergic reaction as defined in CTCEA 5.0, Lumicell should be contacted within 24 hours of the event:

To Lumicell:
[name].
[contact]
Email: [contact]
[contact]

11.3 Expected adverse device effects (associated with the LUM Imaging System)

To date in the Phase 1 and Feasibility Studies, there have been no adverse device events associated with use of LUM Imaging Device. Patients in this trial will be monitored for potential infections, hematomas or other intraoperative or post-operative adverse device events. A list of potential adverse device effects is included in the Investigators Brochure.

12 ADVERSE EVENT REPORTING REQUIREMENTS

12.1 Definitions

12.1.1 Adverse Event (AE)

An adverse event (AE) is any undesirable sign, symptom or medical condition or experience that develops or worsens in severity after starting the first dose of study treatment or any procedure specified in the protocol, even if the event is not considered to be related to the study. The severity of any possible AE observed will be classified per the grading established by the Common Terminology Criteria for Adverse Events (CTCAE) 5.0.

Abnormal laboratory values or diagnostic test results constitute adverse events only if they induce clinical signs or symptoms or require treatment or further diagnostic tests.

12.1.2 Serious adverse event (SAE)

A serious adverse event (SAE) is any adverse event, occurring at any dose and regardless of causality that:

- Results in death
- Is life-threatening. Life-threatening means that the person was at immediate risk of death from the reaction as it occurred, i.e., it does not include a reaction which hypothetically might have caused death had it occurred in a more severe form.
- Requires or prolongs inpatient hospitalization (i.e., the event required at least a 24-hour hospitalization or prolonged a hospitalization beyond the expected length of stay). Hospitalization admissions and/or surgical operations scheduled to occur during the study period, but planned prior to study entry are not considered SAEs if the illness or disease existed before the person was enrolled in the trial, provided that it did not deteriorate in an unexpected manner during the trial (e.g., surgery performed earlier than planned).
- Results in persistent or significant disability/incapacity. Disability is defined as a substantial disruption of a person's ability to conduct normal life functions.
- Is a congenital anomaly or birth defect; or
- Is an important medical event when, based upon appropriate medical judgment, it may jeopardize the subject and require medical or surgical intervention to prevent one of the outcomes listed above. Examples of such medical events include allergic bronchospasm

LUMICELL CONFIDENTIAL

This document is confidential. Do not disclose or use except as authorized.

requiring intensive treatment in an emergency room or at home; blood dyscrasias or convulsions that do not result in inpatient hospitalization, or the development of drug dependency or drug abuse.

Events **not** considered to be serious adverse events are hospitalizations for:

- routine treatment or monitoring of the studied indication, not associated with any deterioration in condition, or for elective procedures
- elective or pre-planned treatment for a pre-existing condition that did not worsen
- respite care

